## Assessment of Efficacy

Study design, sample size, and application of novel questionnaire versions do not allow to sufficiently prove efficacy of the treatment. However, first indicators of efficacy are investigated by pre-/post comparisons of psychological flexibility (AAQ-ABI) and psychological burden (DASS-21). As secondary outcomes, changes in valued living (VQ), self-as-context (SACS), depressive symptoms (PHQ-9), and anxiety symptoms (GAD-7) are examined. Statistically significant changes are considered indicators of efficacy. In addition, number of participants under the cut-offs on DASS-21 (D  $\leq$  10, A  $\leq$  6, S  $\leq$  10), PHQ-9 ( $\leq$  11), and GAD-7 ( $\leq$  11) before and after the therapy are assessed.

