## Statistical Analysis Plan

Missing values are replaced by multiple imputation including all assessed variables. Outliers are identified by visual inspection and inclusion/exclusion is decided on a case-by-case approach. Estimates are calculated based on 95% confidence intervals.

Feasibility (research question 1) is assessed by frequencies fulfilling the predefined cut-offs (see objectives).

The acceptance score of  $> 2$  is evaluated by Wilcoxon-tests for one sample (one-sided) for all versions of the GTS (-P mean of single sessions and entire therapy, -T, and -TP). Significant changes in primary outcomes psychological flexibility (AAQ-ABI) and psychological burden (DASS-21) are assessed with Wilcoxon-tests for paired samples (one-sided);  $p$ -value is Bonferroni-adjusted ( $p = .025$ ). Significant changes in secondary outcomes valued living (VQ), self-as-context (SACS), depressive symptoms (PHQ-9), and anxiety symptoms (GAD-7) are assessed with Wilcoxon-tests for paired samples (one-sided);  $p$ -value is Bonferroni-adjusted ( $p = .0125$ ). Individual changes in primary and secondary outcomes are also based on reliable change indices with a significance level of  $\alpha = .90$  (one-sided).

Sensitivity analyses examine the influence of the baseline variables age, gender, kind of stroke (ischemia vs. hemorrhage), current use of prescribed psychotropic drugs (yes/no), previous mental disorder (yes/no), and previous use of psychotherapy (yes/no) on changes in primary and secondary outcomes. These bivariate associations are investigated by Pearson correlations (for continuous covariates) and Chi tests (for categorical covariates;  $p = .05$ , two-sided) using the difference scores of the outcomes. Likewise, associations between therapy acceptance and the changes in efficacy outcomes (AAQ-ABI, DASS-21, VQ, SACS, PHQ-9 and GAD-7) are exploratively analyzed.

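### Chi-square tests on ungrouped change scores ignore the size and direction of change and, at N = 12, cannot reach p < .05 for a two-level covariate once seven distinct scores occur

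*Combined protocol and SAP*

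**What the plan says.** The Statistical Analysis Plan section introduces these analyses as follows: "Sensitivity analyses examine the influence of the baseline variables age, gender, kind of stroke". The list continues with psychotropic medication, previous mental disorder and previous psychotherapy. The method depends on the type of covariate: "These bivariate associations are investigated by Pearson correlations (for continuous covariates"), and "Chi 2 tests (for categorical covariates"), at a two-sided level of .05. Both are run "using the difference scores of the outcomes".

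Four of the five categorical covariates are written with two levels, for example "kind of stroke (ischemia vs. hemorrhage), current use of prescribed psychotropic drugs (yes/no"). The levels of gender are not stated.

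The section gives no cut-off or grouping for the difference scores. It does plan a categorical view of change elsewhere: "Individual changes in primary and secondary outcomes are also based on reliable change indices". Assessment of Efficacy also counts participants under cut-offs on three questionnaires. Neither is linked to the covariate tests.

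**The concern.** A pre-post difference score is numeric, and the plan treats it so when it correlates age with the same scores. A Chi-square test needs categories. Without a grouping rule, each observed score value becomes its own column, and a change of -6 is as different from -5 as it is from +4. Two problems follow.

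- **Spread-out scores.** The table becomes so sparse that the test cannot reject. A null result then says almost nothing but may be reported as absence of influence.
- **Clustered scores with one participant alone in a category.** The error can go the other way, and false positives can exceed the nominal 5%.

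These are the plan's only tests for five of its six baseline covariates.

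**Working it through.** **Inputs.** N = 12 (Study Design; Selection and Exclusion of Subjects). Two levels for four covariates, two-sided level .05, and ungrouped difference scores of six outcomes (Statistical Analysis Plan). The number of distinct scores, k, is not given, so a range is shown. The plan states no power or p-value for these tests, so there is no figure to reproduce.

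**Tests affected.** 5 categorical covariates × 6 outcomes = 30, of 6 × 6 = 36 in total. If the three DASS-21 subscales are tested separately there are 8 outcomes, giving 5 × 8 = 40 of 48.

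**Floor on p.** For an r × k table, the maximum Pearson Chi-square is N × min(r − 1, k − 1). With two levels this is 12, on k − 1 degrees of freedom. The smallest asymptotic p is therefore P(χ² with k − 1 df ≥ 12). For k = 7 (df 6) this is e⁻⁶(1 + 6 + 18) = .062. Enumeration of all 2 × k tables with N = 12 confirmed the maximum of 12 for every k from 2 to 12.

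| Distinct scores k | 5 | 6 | 7 | 8 | 9 | 10 | 11 | 12 |
|---|---|---|---|---|---|---|---|---|
| Minimum p, two levels | .017 | .035 | .062 | .101 | .151 | .213 | .285 | .364 |

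At k = 12 the statistic is always 12, so p = .364 whatever the data show. If gender had three levels, the maximum would be 24 on 2(k − 1) df. The floor would then be .020 at k = 7, .046 at 8 and .090 at 9.

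**Order and size are not used.** Two constructed data sets, each with a 6/6 split, seven distinct scores and no score shared between groups:

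- Separated: A = −6, −6, −5, −5, −4, −4 (mean −5.0); B = 1, 1, 2, 2, 3, 4 (mean +2.2).
- Equal means: A = −5, −5, −1, −1, 3, 3 (mean −1.0); B = −7, −3, −3, 1, 1, 5 (mean −1.0).

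Both give Chi-square = 12, df 6, p = .062. Exact Mann-Whitney gives p = .002 for the first and 1.0 for the second.

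**Simulation.** The documents give neither an SD of change nor a score step, so both are assumptions. Scores are rounded normal, with 3,000 runs per setting and an exact permutation Mann-Whitney test with midranks. The table shows rejection rates for a true group difference of 2 SD.

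| Setting | Chi-square | Exact Mann-Whitney |
|---|---|---|
| 1-point steps, SD 3–8, splits 6/6 and 4/8 | under 1% | 77–84% |
| 1-point steps, SD 2, splits 6/6 and 4/8 | 2.1–3.9% | 78–80% |
| 1-point steps, SD 2, split 2/10 | 10.1% | 49% |
| 2-point steps, SD 3, splits 6/6 and 4/8 | 7.5–10.3% | 76–80% |
| 2-point steps, SD 5, splits 6/6 and 4/8 | 0.9–1.5% | 77–83% |
| 2-point steps, SD 8, splits 6/6 and 4/8 | 0.1–0.2% | 79–83% |

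With no effect and 1-point steps (6/6 and 4/8), seven or more distinct scores occurred in 41% of runs at SD 2, 82–83% at SD 3 and at least 98% at SD 5–8. With 2-point steps the shares were 10% at SD 3, 67% at SD 5 and 94–95% at SD 8.

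**False positives.** With no effect, 1-point steps and a 1/11 split, Chi-square rejected in 10.4% of runs at SD 2, 3.3% at SD 3 and under 0.5% at SD 5–8.

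**The case against.** The strongest reply is that the authors may have meant a change category, such as reliable change yes/no. A 2 × 2 table at N = 12 can reach p = .0005, so the floor would vanish. That is possible, but the text specifies difference scores and correlates the same scores with age as numbers. If a category was meant, it has to be named, because different categorisations give different results.

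Second, the .062 figure depends on the Pearson statistic, an asymptotic p and 12 complete pairs. This is true:

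- The likelihood-ratio version has a floor above .05 only from 10 distinct scores (.055).
- A permutation p removes the floor.
- With N = 16, which the group size of 8 in the attendance criterion under Objectives would imply, the floor passes .05 only at 10 scores (.067).
- With 10 pairs, which the 20% drop-out target would allow, it passes .05 already at 6 scores (.075).

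None of these restores order. With a permutation p for the same statistic and a 2 SD difference (6/6 and 4/8 splits), rejection is still only 0.1–10.3% at SD 3–8 and 14–20% at SD 2.

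Third, 2 SD is a large assumed effect. At 1 SD the Mann-Whitney test has only 26–33% power, so most results would still be null. That stands, and it is why effect sizes should carry the interpretation. At 1 SD Chi-square rejects in 0–0.5% of runs.

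Fourth, the false-positive risk is narrow: for no-effect rejection above 5%, it needs a one-person category and tightly clustered scores. That also stands.

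Finally, these are sensitivity analyses in a pilot whose Assessment of Efficacy section already says that design, sample size and new questionnaire versions "do not allow to sufficiently prove efficacy of the treatment". This limits the consequence but does not make the test suitable.

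**Conclusion.** The concern holds. As written, the test does not fit its variable. Its loss of order and magnitude does not depend on k, the SD or the way p is computed. The floor of .062 is exact for a two-level covariate, Pearson Chi-square, asymptotic p, N = 12 and seven distinct scores, and it rises with more scores. With six or fewer distinct scores, p < .05 is attainable. How often seven or more occur depends on the assumed spread and score step. The rejection rates likewise rest on assumed SDs and effects.

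The consequence is confined to the covariate sensitivity analyses. The Wilcoxon tests, feasibility cut-offs, acceptance threshold and safety rules do not use these tests. The point should be fixed before analysis but does not threaten the study's main results.

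**What to change.** State first which change variable is tested.

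- **Numeric difference score, as written.** Replace Chi-square with exact Mann-Whitney tests between categories, or Kruskal-Wallis if a covariate has more than two levels. Report a rank-biserial correlation or a median difference with a 95% CI, and keep the correlation for age.
- **Change category.** Name it (for example, reliable change yes/no) and use Fisher's exact test.

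In either case, label the tests exploratory and let effect sizes carry the interpretation. The section also says "Missing values are replaced by multiple imputation including all assessed variables", so one sentence should say how these tests are run with imputed data. Options are exact tests on observed pre-post pairs, or an effect estimate pooled across imputed datasets.

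The plan should also state what small categories allow. The minimum exact two-sided Mann-Whitney p is 2/C(12, n₁): .002 at 6/6, .004 at 4/8, .009 at 3/9, .030 at 2/10 and .167 at 1/11. Power at 2 SD is about 50% with a 2/10 split and zero at 1/11. At 1/11 an exact rank-based interval cannot exceed 1 − .167 = 83% confidence, so that case is better described than tested.

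The cost is SAP wording and a little analysis work, with the same data and no new visits. The drawback is that many of these tests will still be null for moderate effects.

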## Ethics

All participants give written informed consent. The study was approved by the ethics review board of Bielefeld University (EUB-2023-341).

